5.3.3 Risk factor regression analyses

To identify risk factors for the persistence of somatic symptoms in Long COVID we will use longitudinal data from the control group (TAU) within the FAS. Patients from the intervention group (COV.EXPECT, COV.SUPPORT) are excluded because the treatment could bias the results. The risk factors are analysed with a multivariable mixed linear regression with symptom persistence (PHQ-15) as outcome and different risk factors as independent variables, while taking the number of predictors with respect to the sample size into account. The list of possible risk factors includes:

- Age
- Gender
- Chronic physical diseases (SCQ-D)
- BMI
- Smoking
- Education
- Migration background
- PHQ-15 Baseline score
- Depression severity (PHQ-9)
- Illness-related worries (Whiteley-Index-7 [WI-7])
- Expected symptom severity in 6 months (NRS)
- Expected coping with symptoms in 6 months (NRS)
- Catastrophizing (Coping Strategies Questionnaire-Catastrophizing Subscale [CSQ-CAT])
- Illness perception (B-IPQ)
- Life stressors (Perceived Stress Scale-10 [PSS-10])
- Somatosensory Amplification (Somatosensory Amplification Scale [SSAS])
- Alexithymia (Toronto Alexithymia Scale-20 [TAS-20])
- Emotion regulation (Emotion Regulation Questionnaire [ERQ] suppression scale)
- Adverse childhood experiences (Adverse Childhood Experience Questionnaire German version [ACE-D])
- Stigmatization (Stigma)

In case of no significant effects of the interventions on the outcome PHQ-15 in the primary analysis (within the testing of the global effect) an additional analysis will be conducted within observations from all three groups. In the specified risk factor regression model the intervention group (TAU, COV.EXPECT, COV.SUPPORT) will be included as an adjusting variable.

Common risk factors for somatic symptom persistence:

The disease-specific regression analysis from the model to identify risk factors for Long COVID symptoms will be compared to models from the research Unit SOMACROSS to identify shared risk factors across conditions. Also further exploratory analysis should be conducted.

5.3.4 Mediation analyses

In order to analyse whether effects on persistent Long COVID symptoms resulted through changes in dysfunctional symptom expectations or illness-related anxiety, we will conduct causal mediation analyses (CMA). CMA will examine whether in patients receiving COV.EXPECT, changes in the mediating variables at the 6 weeks' assessment predict a reduction in overall somatic symptom severity (PHQ-15) at 3 months (primary outcome) and 6 months. That is to say, the adjusted total treatment effect will be divided into the indirect effect, which describes the treatment effect on persistent long COVID symptoms via the mediators, and the direct effect, which describes the treatment effect not mediated through the mediators. Subsequently, the percentage mediated (PM) can be estimated. Only potential mediator-outcome confounders need to be controlled for due to randomisation and a possible treatment-mediator interaction must be considered. To account for mediator-outcome confounding, we adjust generally for gender and other relevant confounders.

Version 1.0 Page 15 of 18

In our main CMA we include expectations of symptom severity, symptom burden, coping with symptoms, as well as treatment expectations (TEX-Q), and illness-related anxiety (SSD-12) at 6 weeks follow-up as mediating variables. We estimate the effect of the mediating variables on the PHQ-15 at 3 months and will repeat this analysis when 6 month data is available.

The following sensitivity analyses are to be carried out to validate the results and investigate changes in the (in)direct effects and PM with regard to our main mediation model:

Handling of missing values by using the full information maximum likelihood (FIML) approach
in the adjusted model with all confounders.

5.3.5 Sensitivity Analyses

The primary analysis (mixed linear model based on implicit MAR assumptions) will be repeated in the PP set. Furthermore, for the primary analysis a multiple imputation procedure will be conducted in case more than 5% of values are missing for the primary outcome.

Also, a potential effect of recruitment setting will be investigated by including setting as a fixed effect in the primary analysis model.

5.3.6 Subgroup Analyses

The analysis of the subgroups is based on the FAS and thus is as close as possible to the ITT principle. Missing values are not imputed, but the implicit MAR assumption of the analysis model will be used.

Exploratory subgroup analyses will be performed for the primary endpoint by the appropriate interaction tests within the linear mixed regression model used within the primary analysis. The presented p-values are of descriptive nature only (two-sided tests). Relevant subgroups will be identified with a p-value for the interaction < 0.15 (EMA, 2019).

Predefined subgroups are:

- Age (young [≤first tercile] vs. middle aged vs. old [>third tercile])
- Gender (male vs. female)
- Education (≤ 10 years in school vs. > 10 years in school)
- Social support (number of people living in household ≤ 1 vs. > 1)
- Duration of Long COVID (< 1 year vs. ≤ 2 years vs. > 2 years)
- Severity of overall somatic symptoms at baseline (PHQ-15 score minimal/mild/moderate 0-14 vs. severe 15-30)
- Any chronic physical disease (SCQ-D)
- Any chronic mental illness (SCQ-D)
- Depression (PHQ-9 <10 vs. ≥10)
- Anxiety (GAD-7 <10 vs. ≥10)
- Biopsychosocial understanding of disease (yes vs. no; open question B-IPQ)
- Source of recruitment (University Medical Centre Hamburg-Eppendorf vs. Self-help group vs. Social media vs. Medical or physiotherapy practice vs. Other)
- Illness-related anxiety (SSD-12 < 24 vs. ≥ 24)
- Treatment expectations (TEX-Q <5 vs. ≥5)
- Alexithymia (TAS-20 <60 vs. ≥ 61)
- Emotion regulation (ERQ suppression split at median)

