3.1 Confidence Intervals and P Values

For the primary analysis, the significance level is α =0.05 (two-sided). All further analyses are exploratory and will not be adjusted for multiplicity. All applicable statistical tests will be two-sided. All reported confidence intervals (CI) are at 95% level and two-sided.

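### Two subgroup definitions in SAP section 5.3.6 do not work as written: the oldest age group is empty, and a TAS-20 score of 60 belongs to neither alexithymia group

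*SAP*

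**What the plan says.** Section 5.3.6 plans subgroup analyses of the primary endpoint, run as interaction tests within the primary mixed model and based on the full analysis set. The list that follows "Predefined subgroups are" has 16 variables. Two of the entries matter here:

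- "Age (young [≤first tercile] vs. middle aged vs. old [>third tercile"
- "Alexithymia (TAS-20 <60 vs. ≥ 61"

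The section also sets a screening rule, "Relevant subgroups will be identified with a p-value for the interaction < 0.15", with a reference to an EMA guideline. It qualifies the results: "The presented p-values are of descriptive nature only (two-sided tests". Section 3.1 adds, for everything beyond the primary analysis: "All further analyses are exploratory and will not be adjusted for multiplicity".

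Section 5.7 lists alexithymia among six subgroup variables added relative to the trial protocol. The SAP is therefore the place where one expects to find its cut point.

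**The concern.** These bracketed cut points are the operative rules from which the subgroup variables will be coded.

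The age entry pairs a lower limit at the first tercile with an upper limit at the third. Taken literally, it yields two groups, and the oldest patients are merged with the middle third. The interaction test would then compare the youngest third with everyone else, and could not show whether older patients respond differently.

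The alexithymia entry leaves a gap between its two conditions. Patients in the gap have no subgroup value, so a model with that variable would omit them even though they are in the analysis set.

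If either entry is left as it stands, the analyst has to depart from the plan at the time of coding, possibly with outcome data in view. A predefined list is meant to prevent that.

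**Working it through.** **The plan's own sample size.** Inputs from SAP section 2.3: d = 0.5, power 80%, two-sided alpha 5%, loss 25%.

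- Normal approximation: n = 2(1.960 + 0.842)² / 0.5² = 2 × 7.849 / 0.25 = 62.8, so 63 per group. The two-sample t-test gives 63.8, so 64 per group, as stated.
- 64 / 0.75 = 85.3, so 86 per group, and 3 × 86 = 258, as stated.

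The figure reproduces. It is used below only to give the subgroup sizes a scale.

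**Age.** Two cut points divide a sample into thirds. There are two ways to read the word tercile:

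1. As a cut point. The first tercile is the 1/3 quantile, the second the 2/3 quantile and the third the maximum. No age exceeds the maximum.
2. As the third itself. The third tercile is then the top third, and nobody lies above the top third.

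Under both readings the old group has 0 patients. With 258 patients and no ties:

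| Rule | Young | Middle aged | Old |
|---|---|---|---|
| As written | 258/3 = 86 | 2 × 86 = 172 | 0 |
| Oldest group starting above the second tercile | 86 | 86 | 86 |

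With the 192 patients expected to have 3-month data, the rule as written gives 64/128/0. In an illustrative sample of 258 simulated ages, rounded to whole years, the rule as written gave 86/172/0 and the corrected rule 86/91/81. The departure from equal thirds comes from tied ages.

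**TAS-20.** One group needs a score below 60 and the other a score of 61 or more. Among whole-number scores, only 60 meets neither condition. The SAP does not give the share of patients scoring 60. If it were 1% to 4%, which is purely an assumption, that would be 0.01 × 258 = 2.6 to 0.04 × 258 = 10.3, or about 3 to 10 patients.

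Other score cuts in the same list leave no gap: PHQ-9 and GAD-7 at 10, SSD-12 at 24 and TEX-Q at 5 each use the same number on both sides. This points to a slip rather than a convention of the document.

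**The p < 0.15 screen.** Inputs: 16 variables, threshold 0.15, no true interaction, one test per variable (the last is assumed).

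- Expected flags: 16 × 0.15 = 2.4. This does not depend on correlation between the variables.
- Chance of at least one flag if the tests are independent: 1 − 0.85¹⁶ = 0.926.
- Chance of at least two: 0.716. Chance of at least three: 0.439.
- With correlated subgroup variables (simulation, 2000 runs, 192 patients, three arms, assumed latent correlation 0.3 / 0.5 / 0.7), the chance of at least one is 0.90 / 0.84 / 0.79. The mean number of flags stays at about 2.4.

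**The case against.** **The slips are obvious and would be put right in practice.** The age entry names three groups and uses terciles, so thirds are plainly meant, and an empty category would show at the first tabulation. This stands as a reason to keep the point small. A reader might infer that the trial will fail to examine older patients; that follows only if the text is carried out mechanically. It does not make the text correct, and no other part of the SAP repairs it.

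**The place for 60 is not ours to choose.** This stands. The text supports splitting below versus from 60 as readily as up to 60 versus from 61, and the SAP does not reproduce the scoring rule. It shows only that 60 has to go somewhere.

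**Other entries are loose too.** The middle band for duration of Long COVID has no lower limit, and the gender subgroup has two levels where section 5.1.1 lists three. The duration bands resolve when read in order, and a two-level gender comparison may be deliberate. Neither produces an empty group or an evident gap in a numeric scale.

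**The p < 0.15 rule.** A reader might go further and infer that the rule is an error that will almost surely label noise as relevant, and that it should be deleted or replaced by a Holm adjustment. The documents do not support that:

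- Section 5.3.6 introduces the tests with "Exploratory subgroup analyses will be performed for the primary endpoint by the appropriate interaction tests" and calls their p-values descriptive, and section 3.1 states that nothing beyond the primary analysis is adjusted. The lenient threshold is a disclosed choice, fixed in advance, with no confirmatory claim attached. Whether the cited guideline supports it cannot be judged from the SAP.
- The 93% figure needs independent tests and no true interaction anywhere. Depression, anxiety, illness-related anxiety and baseline symptom severity plausibly overlap, and under the assumed correlations the chance is about 79% to 90%.
- Holm would start at 0.05/16 = 0.003 in a trial sized for a main effect of d = 0.5, leaving little ability to detect an interaction.

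What remains is modest: the SAP calls flagged subgroups relevant without telling readers how many flags chance alone would produce.

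**Conclusion.** Two of the 16 subgroup definitions are wrong as written. The age rule leaves the old group empty under either reading of tercile and gives about 86/172/0 of 258; this assumes only that the rule is applied literally and that ties are ignored. The TAS-20 rule leaves a score of 60 unassigned, for a number of patients that the SAP does not allow one to calculate. Both are minor. They touch two exploratory analyses and leave the primary and secondary analyses unchanged.

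The p < 0.15 screen is not an error. The supportable statement is that about 2.4 of 16 flags are expected if no interaction is real, with a chance of at least one of about 93% under independence and less if the variables are correlated.

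**What to change.** 1. Age: define the groups as up to and including the first tercile, above the first up to and including the second, and above the second.
2. Alexithymia: assign a score of 60 to one of the two groups according to the scale's scoring rule, and record that choice before unblinding.
3. Optional: keep the p < 0.15 screen, report all 16 interaction estimates with 95% confidence intervals whether flagged or not, and add a sentence that about 2.4 flags are expected by chance if there is no true interaction.

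The first two items change SAP wording only, with no new data and no effect on sample size or the primary analysis. The third adds one table and one sentence to the report.

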2.2 Randomisation

Patients are randomised to COV.EXPECT, COV.SUPPORT or TAU with an allocation ratio of 1:1:1. The randomisation is stratified by sex with a block randomisation procedure with varying block length. The randomisation list was generated using R software (R Project for Statistical Computing) by an independent member of the biostatistics unit and uploaded in REDCap (Research Electronic Data Capture), a software for building and managing online surveys and databases.

The randomisation is performed directly after verification that no inclusion criteria are violated and no exclusion criteria are met. Baseline data are collected afterwards.

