2.3 Sample Size

The trial is powered for the comparison between the COV.EXPECT group and the TAU group. The type one error (alpha) is not adjusted for multiplicity due to the closed testing principle. A between-group effect size of d=0.5 is expected between COV.EXPECT and TAU for the change from baseline in the PHQ-15 score at 3 months. To detect this effect with a power of 80% and using a two-sided alpha of 5%, 64 patients in each group will be required, resulting in a total sample size of N=192. Assuming a loss to follow-up between baseline and 3 months (time point for primary outcome) of 25%, this results in N=258 randomised patients. Assuming that 50% of the screened patients meet the inclusion criteria, a total of N=516 patients will be assessed for eligibility.

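### The interaction tests for age and seven scale scores use only categorised moderators, an avoidable loss of power in exploratory analyses

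*SAP*

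**What the plan says.** SAP section 5.3.6 plans exploratory subgroup analyses of the primary endpoint by "appropriate interaction tests within the linear mixed regression model" of the primary analysis. It calls the p-values descriptive and labels a subgroup relevant when the interaction p-value is below 0.15. Eight of the sixteen listed moderators are age or scale scores, and each appears only in categories:

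- Age is cut at sample terciles.
- ERQ suppression is cut at the sample median: "Emotion regulation (ERQ suppression split at median".
- PHQ-15, PHQ-9, GAD-7, SSD-12, TEX-Q and TAS-20 are cut at fixed values.

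The full values are available. Section 5.1.1 lists age in years and the PHQ-15, PHQ-9, GAD-7, SSD-12 and TEX-Q at baseline, and section 5.3.3 uses the TAS-20 and the ERQ suppression scale as risk factors. Baseline PHQ-15 is already a covariate in the primary model (section 5.3.1). No continuous moderator by treatment term is planned anywhere.

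Section 2.3 gives power for one main effect only: "The trial is powered for the comparison between the COV.EXPECT group and the TAU group".

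**The concern.** Categories suit a forest plot, but the p-value that decides which subgroups are called relevant does not need them. Cutting a score treats all patients on one side as alike and discards the differences among them. The trial is not sized for interactions, so these tests are weak to begin with, and an avoidable loss makes a true effect modifier easier to miss. That matters most for illness-related anxiety and treatment expectations (SSD-12 and TEX-Q), which are also mediators in section 5.3.4. A smaller issue is that the age and ERQ cuts depend on who was recruited, so a subgroup found with them has no fixed definition in another sample.

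**Working it through.** **The plan's own figure.** Section 2.3 states "A between-group effect size of d=0.5 is expected between COV.EXPECT and TAU" and "with a power of 80% and using a two-sided alpha of 5%, 64 patients in each group will be required".

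- Normal approximation: 2 × (1.960 + 0.842)² / 0.5² = 62.8, so 63 per group.
- Exact t test: power is 0.795 at 63 and 0.801 at 64, so 64 per group and 3 × 64 = 192 in total.
- Dropout of 25%: 64 / 0.75 = 85.3, so 86 per group and 3 × 86 = 258.

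The stated sizes reproduce. They concern the main effect; the SAP gives no power for interactions.

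**Information kept by a split.** Assumptions not in the SAP: normal moderator, linear interaction, residual SD 1. A two-way split with share p below the cut c keeps φ(c)² / [p(1 − p)] of the information in the linear term. Terciles keep the between-category variance: each outer third has mean ±3 × 0.3636 = ±1.091, so (2/3) × 1.091² = 0.793. The shares below the fixed cut-offs are not in the SAP and are varied here.

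| Split | Kept | Lost |
|---|---|---|
| Median (ERQ) | 0.1592 / 0.25 = 0.637 (= 2/π) | 36% |
| Terciles (age) | 0.793 | 21%, plus extra degrees of freedom |
| Cut-off 40/60 | 0.622 | 38% |
| Cut-off 30/70 | 0.576 | 42% |
| Cut-off 20/80 | 0.490 | 51% |
| Cut-off 10/90 | 0.342 | 66% |

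For a uniform moderator a two-way split keeps 3p(1 − p). At the median that is 0.75 (25% lost), and terciles keep 8/9 (11% lost). The advantage over the normal case holds for near-even splits only: at 20/80 the uniform moderator keeps 3 × 0.16 = 0.48, about the same.

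**Power.** Illustrative comparison of COV.EXPECT with TAU, n = 64 per arm. If the treatment effect changes by b per SD of a normal moderator, its mean differs by 1.596b between the upper and lower halves. For a difference of 0.5 SD, b = 0.5 / 1.596 = 0.313. The noncentrality is b²n/2 = 3.14 for the continuous term and 3.14 × 0.637 = 2.00 for the median split.

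| Difference between halves | Threshold | Continuous | Median split | Terciles (2 df) |
|---|---|---|---|---|
| 0.5 SD | 0.05 | 43% | 29% | 27% |
| 0.5 SD | 0.15 | 63% | 49% | 47% |
| 0.25 SD | 0.05 | 14% | 11% | 10% |
| 0.25 SD | 0.15 | 30% | 25% | 24% |

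A simulation of the 0.5 SD case (10,000 runs) gave 41% and 28% at 0.05, and 61% and 48% at 0.15. The simulated efficiency of the median split was 0.636.

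**Three arms.** If only COV.EXPECT carries the interaction, the joint test across three arms of 64 has noncentrality 64 × b² × 2/3 = 4.19. At 0.15 its power is 64% continuous, 49% median split and 47% terciles (4 df). The comparison is much the same as with two arms.

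**The case against.** The strongest reply is that this is a choice, not a mistake. The categories are set in advance, the analyses are labelled exploratory, the p-values are called descriptive, and the 0.15 threshold partly offsets low power. All of that stands, and it limits the weight of the point. It does not make the loss necessary, because the label of relevance still rests on the p-value.

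The linear test also assumes something. If the effect truly steps at the cut, the split loses nothing and the linear test can be the weaker one. By the same correlation formula, a linear term fitted to a step at the median of a normal moderator keeps only about 64%. This stands as the price of the change.

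Three stronger readings are tempting, and the SAP does not support them:

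- A reader might infer that about a third of the information is lost in every subgroup. That figure fits the ERQ median split under normality. The other losses depend on distributions the SAP does not give, and normality is doubtful for PHQ-15, since section 2.1 admits only patients scoring 10 or more at entry.
- A reader might infer that none of the subgroups carries over to another sample. Six of the eight moderators have fixed numerical cut-offs that do; only age and ERQ depend on the sample.
- A reader might infer a larger gain from a stronger interaction. One of 0.4 SD per SD implies a difference of 0.4 × 1.596 = 0.64 SD between halves, more than the whole expected main effect of 0.5.

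Finally, the power figures come from a single-time-point simplification, whereas the planned model has repeated measurements. They illustrate the comparison and are not the power of the SAP's tests.

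**Conclusion.** The point holds as a cheap improvement. Section 5.3.6 contains no contradiction on this matter, and neither the primary analysis nor its conclusion is affected. For age and the seven scale scores, the planned tests use less information than the trial collects. With a normal moderator and a linear interaction the loss is about 36% for ERQ, about 21% plus degrees of freedom for age, and 36% to 66% for the fixed cut-offs over the range 50/50 to 10/90. The practical gain depends on the size of the interaction: about 14 percentage points of power at the 0.15 threshold when the effect differs by 0.5 SD between halves (63% against 49%), and about 5 points at 0.25 SD (30% against 25%), where both tests are weak.

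**What to change.** In section 5.3.6, state that for age, PHQ-15, PHQ-9, GAD-7, SSD-12, TEX-Q, TAS-20 and ERQ suppression the interaction p-value comes from the continuous moderator by treatment term in the primary mixed model, with the moderator's own linear term included (baseline PHQ-15 is already there). Keep the listed categories for the forest plot and the descriptive estimates by subgroup.

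The cost is a sentence or two of SAP wording and a change of variable in the code, with no extra patients or data. The downside is that a linear interaction is assumed. The category estimates help the reader check this, and a spline could be used if they suggest a clear departure.

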5.4 Safety Evaluation

Adverse events (AE) and serious adverse events (SAE) are analysed descriptively, i.e. event rates with percentages on patient level and event numbers on event level will be given in total and by randomised treatment in the EFS.

Version 1.0 Page 16 of 18

All AEs are reported, whether or not they are considered to be related to treatment. If not stated otherwise, AEs are counted over the complete trial duration, i.e. from randomisation up to 6 months.

